10.2.5. Investigator Immediate Reporting Requirements

All SAEs and pregnancies must be reported to the sponsor or the sponsor's designee immediately, and no later than 24 hours of becoming aware of the event.

The initial SAE report should be as complete as possible (Section 10.2.2.5); however, reporting should not be delayed in order to obtain more information. The SAE should also be entered on the applicable eCRF. All follow-up information should be reported within 24 hours of the Investigator's awareness of the information. The Investigator is required to provide follow-up information in response to queries from the sponsor or the sponsor's designee. Hospital discharge summaries should be provided for subjects who are hospitalized and autopsy findings, if available, should be provided for subjects who die.

All SAEs and pregnancies should be reported to the contact indicated on the SAE form and entered on the applicable eCRF.

10.2.6. Investigator Notification to Local Institutional Review Boards/Ethics Committees

The Investigator must notify their local Institutional Review Board (IRB)s/ECs about certain AEs including suspected unexpected serious adverse reactions (SUSARs) in accordance with their IRBs'/ECs' policies and procedures and Good Clinical Practice (GCP)/International Conference on Harmonisation (ICH) guidelines.

10.2.7. Sponsor Responsibilities

The sponsor or its designee will be responsible for reporting all AEs, SAEs and SUSARs to the appropriate regulatory authorities, Investigators, and Central IRBs/ECs in accordance with all applicable regulations and guidance documents.

11. STATISTICS

11.1. Sample Size Determination

The sample size of up to approximately 200 subjects assumes that 10-15% of subjects in an ongoing sacituzumab govitecan parent studies will rollover to this study upon closure of the parent study.

11.2. Populations for Analyses

All Treated Subjects: All subjects who received at least one dose of sacituzumab govitecan.

11.3. Statistical Analyses

These analyses will be presented by cancer types and histology when deemed appropriate and by the overall study population. **CCI**

11.3.1. Endpoints

The primary endpoints are as follows:

- Percentage of participants experiencing any AE
- Percentage of participants experiencing any SAE
- Percentage of participants experiencing any laboratory abnormality

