2. STUDY OBJECTIVES AND PURPOSE

2.1. Primary Objective

Evaluate long-term safety in subjects with metastatic solid tumors that are benefiting from continuation of therapy with sacituzumab govitecan.

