3. INVESTIGATIONAL PLAN

3.1. Overall Study Design

This is a Phase 4, open-label, longitudinal cohort, rollover study designed to evaluate long-term safety in subjects with metastatic solid tumors that are benefiting from continuation of therapy with sacituzumab govitecan. Only subjects who continue to receive clinical benefit from continuation of sacituzumab govitecan therapy and are tolerating therapy at the time of enrollment are eligible for this study. Subjects enrolled may continue to receive sacituzumab govitecan at the dose that they were receiving in the parent study at the time of consenting to participate in this rollover study. No dose escalation beyond the dose the subject was receiving in the parent study at the time of consenting to participate in this rollover study is permitted. Subjects who continued to receive sacituzumab govitecan in a parent study after disease progression (PD) may continue to receive sacituzumab govitecan in this rollover study. No subject will receive more than 10 mg/kg dose of sacituzumab govitecan in this rollover study. Subjects may continue to receive sacituzumab govitecan until they experience toxicity, disease progression with no evidence of clinical benefit, loss of clinical benefit, withdrawal of consent, lost to follow-up, or sponsor termination of the study is documented. Subjects of childbearing potential will be followed for Safety Follow-up after study drug discontinuation. Subjects with ongoing adverse events (AEs) or serious adverse events (SAEs) will be followed for Safety Follow-up after EOT.

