11.3.3. Safety Analyses

Safety analyses will be based on All Treated Subjects. All safety analyses will be presented by cancer types and histology when deemed appropriate. Safety data will be summarized using descriptive statistics. Categorical variables will be summarized by number and percentage. Continuous variables will be summarized using n (number of subjects with available data), mean, standard deviation, median, upper and lower quartiles, and range (minimum and maximum), unless otherwise specified.

A treatment-emergent AE will be defined as any AE that begins on or after the date of first dose of study drug up to the date of last dose of study drug plus 30 days. Treatment-emergent laboratory abnormalities will be defined as values that increase at least 1 toxicity grade from baseline at any time after baseline up to and including the date of last dose of study drug plus 30 days. Treatment-emergent AEs and SAEs and clinical laboratory test results will be summarized. Study drug exposure and concomitant medications will also be summarized.

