1. INTRODUCTION

The purpose of this Statistical Analysis Plan (SAP) is to describe the procedures and the statistical methods that will be used to analyze, and report results for study IMMU-132-14: “Open-label Rollover Study to Evaluate Long-term Safety in Subjects with Metastatic Solid Tumors that are Benefiting from Continuation of Therapy with Sacituzumab Govitecan”. This SAP incorporates the original version of the protocol, dated as 16Dec2019. The focus of this SAP is for the final analysis specified in the study protocol.

This SAP provides a comprehensive and detailed description of the objectives, definitions of endpoints, statistical and analytical methods used to evaluate the specified safety endpoints. There is no efficacy analysis for this study.

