2. STUDY OBJECTIVES AND ENDPOINTS

2.1. Primary Objectives and Endpoints

The primary objective is to evaluate long-term safety in subjects with metastatic solid tumors that are benefiting from continuation of therapy with sacituzumab govitecan.

The corresponding endpoints are:

- Safety evaluated on adverse events and serious adverse events, laboratory assessments, study drug exposure and concomitant medications

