6.2. Adverse Events

Treatment-emergent adverse events (TEAEs) are defined as any AEs that begin or worsen on or after the start of study drug through 30 days after the last dose of study drug. All AEs will be coded using Medical Dictionary for Regulatory Activities (MedDRA). The severity will be graded based on the National Cancer Institute's (NCI) Common Terminology Criteria for Adverse Events (CTCAE) v5.0. Only TEAEs will be summarized and will be referred to as AEs hereafter.

The frequency and severity of AEs, classified by MedDRA, will be summarized using MedDRA Preferred Term (PT) and System Organ Class (SOC). An AE that occurs more than once within each subject will be counted only once in the summaries, i.e., where a subject has the same adverse event, based on preferred terminology, reported multiple times, the subject will only be counted once at the preferred terminology level in adverse event summary tables. Where a subject has multiple adverse events within the same system organ class, the subject will be counted only once at the system organ class level in adverse event summary tables. When reporting adverse events by NCI-CTCAE grade, summary tables will be provided using the worst NCI-CTCAE grade.

The following AE summary tables will be provided:

- Overall Summary of Treatment-Emergent Adverse Events
- Summary of Treatment-Emergent Adverse Events by SOC and PT
- Summary of Treatment-Emergent Adverse Events Reported $\geq 10\%$ by Preferred Term
- Summary of Treatment-related Treatment-Emergent Adverse Events by SOC and PT
- Summary of Treatment-Emergent Serious Adverse Events by SOC and PT
- Summary of Treatment-Emergent Serious Adverse Events Reported $\geq 2\%$ by Preferred Term
- Summary of Treatment-related Treatment-Emergent Serious Adverse Events by SOC and PT
- Summary of Treatment-Emergent Adverse Events by Worst NCI-CTCAE Grade, SOC and PT
- Summary of Treatment-related Treatment-Emergent Adverse Events by Worst NCI-CTCAE Grade, SOC and PT
- Summary of NCI-CTCAE Grade 3 or Higher Treatment-Emergent Adverse Events by SOC and PT
- Summary of NCI-CTCAE Grade 3 or Higher Treatment-Emergent Adverse Events Reported $\geq 5\%$ by Preferred Term
- Summary of Treatment-related Treatment-Emergent Adverse Events with NCI-CTCAE Grade 3 or Higher by SOC and PT

- Summary of Treatment-Emergent Adverse Events Leading to Dose Reduction by SOC and PT

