6.3. Adverse Events of Special Interest (AEOSI)

In addition to analyses of AEs, adverse events of special interest (AEOSI) will be assessed. Definitions of AEOSI, as currently defined, are provided in Table 1, including but not limited to the listed. For AEOSI, frequency tables will be generated, showing overall summary of AEOSI, Summary of AEOSI by SOC and PT, Serious AEOSI by SOC and PT, AEOSI leading to study drug discontinuation by SOC and PT, AEOSI leading to dose modification by SOC and PT, Grade 3 or higher AEOSI by SOC and PT, treatment-related AEOSI (by a worst CTCAE grade of 3, 4, or 5, ≥ 3 and any grade) by SOC and PT. Corresponding listings will also be produced. Please see the lists at the end of this section for details.

Table 1: Definitions of Adverse Events of Special Interest

Adverse Event of Special Interest	Definition
Diarrhea	Preferred term: diarrhea
Neutropenia+	Preferred terms: neutropenia, neutrophil count decreased, febrile neutropenia
Febrile neutropenia	Preferred term: febrile neutropenia
Infections	SOC: infections and infestations
Neuropathy+	Preferred term: gait disturbance, hypoesthesia, muscular weakness, neuropathy peripheral, paresthesia, and peripheral sensory neuropathy
Hypersensitivity+*	Hypersensitivity SMQ (broad) and Anaphylactic Reactions SMQ (broad)*
Pulmonary events+	Interstitial lung disease SMQ (narrow)

All definitions based on MedDRA vs 20.0 or higher, SMQ=Standard MedDRA Query

+ Grouped AE terms

* For the category of Hypersensitivity+, only events whose onset dates are on the day of or 1 day after an infusion are included.

The following AEOSI tables will be provided:

- Overall Summary of Adverse Events of Special Interest
- Summary of Adverse Events of Special Interest by SOC and PT
- Summary of Serious Adverse Events of Special Interest by SOC and PT
- Summary of Adverse Events of Special Interest with NCI-CTCAE Grade 3 or Higher by SOC and PT
- Summary of Treatment-related Adverse Events of Special Interest with NCI-CTCAE Grade 3 or Higher by SOC and PT
- Summary of Adverse Events of Special Interest Leading to Dose Reduction by SOC and PT

- Summary of Treatment-related Adverse Events of Special Interest Leading to Dose Reduction by SOC and PT
- Summary of Adverse Events of Special Interest Leading to Dose Interruption by SOC and PT
- Summary of Treatment-related Adverse Events of Special Interest Leading to Dose Interruption by SOC and PT

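### Low-cost improvement: no visible safety table relates SAEs, Grade 3 or higher AEs or AEOSI to time at risk, although treatment is open-ended and long-term safety is the only objective

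*Protocol*

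**What the plan says.** Protocol 2.1 has one objective: "Evaluate long-term safety in subjects with metastatic solid tumors" who are benefiting from continued therapy. Protocol 3.1 sets no treatment length: "Subjects may continue to receive sacituzumab govitecan until they experience toxicity", or until another listed reason for stopping applies.

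Protocol 11.3.1 defines three primary endpoints, all percentages of participants; the one for serious events is "Percentage of participants experiencing any SAE". Protocol 11.3.3 adds: "Categorical variables will be summarized by number and percentage". SAP 2.1 words the endpoint more broadly: "Safety evaluated on adverse events and serious adverse events, laboratory assessments, study drug exposure and concomitant medications".

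SAP 6.2 counts a subject once per preferred term or system organ class. Its tables are of the type "Summary of NCI-CTCAE Grade 3 or Higher Treatment-Emergent Adverse Events by SOC and PT". For AEOSI, SAP 6.3 says that "frequency tables will be generated, showing overall summary of AEOSI" and further breakdowns. SAP 6.1 summarizes duration of treatment on its own, including numbers treated for at least 3, 6, 12 and 24 months. SAP 5.1 allows optional displays by dose level, cancer type and histology.

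SAP 6.4 plans two death summaries: all-cause, with no stated window, and deaths within 30 days of last dose.

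Two limits apply to this reading. Text after the first sentence of Protocol 11.3 is redacted. The SAP also describes itself as written for an early protocol: "This SAP incorporates the original version of the protocol, dated as 16Dec2019".

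**The concern.** When subjects stay on drug for very different times, the proportion who ever have an event depends on both the event rate and the length of observation. A reader of the any-SAE percentage cannot tell a frequent hazard over a short time from a modest hazard over a long time. Nor can the reader see whether risk rises, falls or stays level with continued treatment, which is what a long-term safety study is best placed to show.

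The same applies to any display by dose level, cancer type or histology. Groups with identical risk can show different percentages only because one stayed on drug longer.

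For deaths, an all-cause percentage with no window would use all treated subjects as its denominator, although late deaths are not captured equally in all of them.

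**Working it through.** **Inputs.** From the documents: up to about 200 subjects (Protocol 3.2, 11.1); a treatment-emergent window to last dose + 30 days, taken as about 1 month (SAP 6.2); duration cut-points of 3, 6, 12 and 24 months (SAP 6.1). The documents give no event rate, expected duration or precision target, so there is no plan figure to reproduce. Assumed: a constant first-SAE rate L per month and, where durations vary, exponential stopping for other reasons with mean m months.

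**1. Same risk, different duration.** P(any SAE) = 1 − exp(−L(t + 1)) for t months on drug. For L = 0.05 and t = 3: 1 − exp(−0.20) = 0.181.

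| L per month | 3 months | 12 months | 24 months |
|---|---|---|---|
| 0.02 | 8% | 23% | 39% |
| 0.05 | 18% | 48% | 71% |
| 0.10 | 33% | 73% | 92% |

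**2. Two groups with equal risk, mean 3 and 12 months on drug.** P = 1 − exp(−L) × (1/m)/(1/m + L). At L = 0.02: 7.5% and 21.0%. At L = 0.05: 17.3% and 40.5%. The gap is entirely duration.

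**3. One percentage, many rates.** Suppose 60 of 200 subjects (30%) have an SAE. At a mean time at risk of 3, 6, 12 and 24 months the person-time is 50, 100, 200 and 400 patient-years (200 × months/12). The rates are 120, 60, 30 and 15 per 100 patient-years.

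**4. Would a rate be precise enough?** With n = 200, the probability of being at risk and event-free at t is exp(−Lt) up to 1 month and exp(−Lt) × exp(−(t − 1)/m) after that. Expected first SAEs are L times the person-months in each interval. The exact Poisson CIs use the total rounded to a whole number.

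| L, m | 0–3 | >3–6 | >6–12 | >12 months | Total / person-months | 95% CI per month |
|---|---|---|---|---|---|---|
| 0.02, 6 | 10.5 | 6.2 | 5.6 | 2.7 | 25.0 / 1248 | 0.013–0.030 |
| 0.02, 12 | 11.0 | 8.2 | 10.5 | 12.2 | 41.9 / 2095 | 0.014–0.027 |
| 0.05, 6 | 25.2 | 13.6 | 10.8 | 4.0 | 53.7 / 1073 | 0.038–0.066 |
| 0.05, 12 | 26.5 | 18.0 | 20.2 | 16.5 | 81.1 / 1622 | 0.040–0.062 |

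The overall rate is usable. The last interval is thin: 3 events in about 134 person-months gives 0.005–0.065.

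**5. Deaths.** After the end-of-treatment visit, only subjects of childbearing potential or with ongoing AEs or SAEs enter Safety Follow-up, and they may decline it in writing (Protocol 3.5). The others have reached end of study (Protocol Table 1, footnote b). Protocol 10.2.3 asks for deaths more than 30 days after last dose or start of alternative therapy, whichever is later, if they are judged related. Capture of late deaths therefore depends on follow-up status and on causality. Deaths up to 30 days after last dose are largely free of this.

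**The case against.** The strongest reply is that nothing is broken. The study is single-arm and descriptive, its endpoints are defined as percentages, and the planned tables deliver them. No test or decision rests on a rate. Duration is reported in SAP 6.1, and treatment dates (SAP 5.3) and event listings (SAP 6.2, 6.3) would let someone reconstruct person-time. All of that stands, and it is why this is an improvement and not a correction. What remains is that a reader of the tables does not see events against time.

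A second reply is that an overall rate cures the problem only if the hazard is roughly constant. This also stands. Protocol 1.3.4 places neutropenia and diarrhea in the first cycle of treatment, and this cohort has passed that point and must be tolerating therapy, so the shape of the hazard after rollover is unknown. Overall rates can then still differ between groups because of duration. Interval rates are needed beside the overall rate, and rates for individual AEOSI carry the same caveat.

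A third reply concerns deaths: SAP 6.4 already plans the 30-day summary. That is correct, and it reduces the death point to a minor one.

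A reader might also infer that the sponsor plans no time-based analysis at all. The documents do not support that. Part of Protocol 11.3 is redacted and the visible SAP was written for the original protocol, so the point covers only the visible tables.

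**Conclusion.** The point holds as a worthwhile low-cost improvement. The sole objective is long-term safety under open-ended treatment, and no visible table in SAP 6.2 or 6.3 relates events to time at risk. Under assumed constant rates of 0.02 to 0.10 per month, the any-SAE percentage varies by a factor of roughly 3 to 5 between 3 and 24 months on drug. At 0.05 per month it is 18%, 48% and 71% at 3, 12 and 24 months. These sizes rest wholly on assumed rates, durations and a constant hazard.

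Two stronger readings are tempting and should be resisted. One is that the percentage endpoints are wrong: they are valid descriptive measures and match the protocol. The other is that the death analysis is unsound: only the all-cause summary lacks a window, the 30-day summary beside it is sound, and SAP 6.4 does not itself state that the all-cause summary is a percentage (SAP 5.1 implies it).

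**What to change.** Keep all planned percentages.

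- **SAP 6.2, overall rate.** For any treatment-emergent SAE and any Grade 3 or higher AE, add an exposure-adjusted incidence rate: subjects with a first event divided by person-time. Person-time runs from first dose in this study to the earliest of first event, last dose + 30 days, death, study exit or data cut-off. Give an exact Poisson 95% CI.
- **SAP 6.2, interval rates.** For the same two outcomes, give rates for 0–3, >3–6, >6–12 and >12 months. Label the time axis as time since rollover entry, among subjects still at risk and event-free. It is not total time on drug, because every subject enters with exposure from a parent study.
- **SAP 6.3, optional.** Overall rates for each AEOSI, with the caveat that they are fully interpretable only if the hazard is roughly constant.
- **Subgroup displays.** Wherever dose level, cancer type or histology is shown, put the overall rate beside the percentage.
- **SAP 6.4, minor.** Make deaths within 30 days of last dose the main death percentage. Report later deaths as counts or a listing only. Note that their capture depends on Safety Follow-up status, including written opt-out, and on the relatedness rule in Protocol 10.2.3. No split by follow-up group is needed, since the groups overlap.

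The cost is SAP wording plus 2 overall rates and 8 interval rates (2 outcomes × 4 intervals), with 7 more if the AEOSI in SAP Table 1 are included. Dose and event dates are already needed for SAP 6.1 to 6.3, so no new data are required. The drawback is imprecision: about 3 to 16 first SAEs beyond 12 months under the assumed rates, and wide intervals for rarer AEOSI.

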11.3.2. Efficacy Analyses

Efficacy will not be analyzed.

11.3.3. Safety Analyses

Safety analyses will be based on All Treated Subjects. All safety analyses will be presented by cancer types and histology when deemed appropriate. Safety data will be summarized using descriptive statistics. Categorical variables will be summarized by number and percentage. Continuous variables will be summarized using n (number of subjects with available data), mean, standard deviation, median, upper and lower quartiles, and range (minimum and maximum), unless otherwise specified.

A treatment-emergent AE will be defined as any AE that begins on or after the date of first dose of study drug up to the date of last dose of study drug plus 30 days. Treatment-emergent laboratory abnormalities will be defined as values that increase at least 1 toxicity grade from baseline at any time after baseline up to and including the date of last dose of study drug plus 30 days. Treatment-emergent AEs and SAEs and clinical laboratory test results will be summarized. Study drug exposure and concomitant medications will also be summarized.

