3.4. End of Treatment

After discontinuation of treatment (See Section [5.3](#)), all subjects must complete an end of treatment (EOT) visit approximately 30 days after the last dose of the study drug. Data should be entered into the EOT electronic case report form (eCRF).

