Grade 4 neutropenia \geq 7 days, OR	First	25% dose reduction and administer G-CSF
Grade 3-4 febrile neutropenia, OR	Second	50% dose reduction
At time of scheduled treatment, Grade 3 or 4 neutropenia that delays dosing by 2 or 3 weeks for recovery to \leq Grade 1	Third	Discontinue treatment
At time of scheduled treatment, Grade 3 or 4 neutropenia that delays dosing beyond 3 weeks for recovery to \leq Grade 1	First	Discontinue treatment
Severe nonneutropenic toxicity		
Grade 4 nonhematologic toxicity of any duration, OR	First	25% dose reduction
Any Grade 3 or 4 nausea, vomiting, or diarrhea due to treatment that is not controlled with antiemetics and antidiarrheal agents OR	Second	50% dose reduction
Other Grade 3 or 4 nonhematologic toxicity persisting $>$ 48 hours despite optimal medical management, OR	Third	Discontinue treatment
At time of scheduled treatment, Grade 3 or 4 nonneutropenic hematologic or nonhematologic toxicity that delays dose by 2 or 3 weeks for recovery to \leq Grade 1		
In the event of Grade 3 or 4 nonneutropenic hematologic or nonhematologic toxicity that does not recover to \leq Grade 1 within 3 weeks	First	Discontinue treatment
Infusion-Related Toxicities		
Grade 2 or Grade 3 infusion-related reaction despite optimal management	Recurrent	Discontinue treatment
Grade 4 infusion-related reaction	First	Discontinue treatment

G-CSF = granulocyte colony-stimulating factor; NCI-CTCAE = National Cancer Institute-Common Terminology Criteria for Adverse Events

Refer to Section 10.2.2.6 for the NCI-CTCAE severity grading details.

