6.4. Concomitant Medications

Medications initiated prior to the first dose of study drug will be recorded as prior medications with medications initiated following receipt of the first dose of study drug until 30 days after treatment discontinuation will be captured as concomitant medications. Medication information will be entered in the appropriate eCRF with information regarding dose, indication, route of administration and dates of administration. Medications used for prophylaxis of anticipated study drug adverse events as outlined in the protocol should be documented with rationale for prophylactic intent.

Subjects must avoid the use of osteopathic traditional medicine and any other traditional medicine during the study.

No anti-cancer therapies, aside from the study drug are permitted during this study. However, palliative and/or supportive medications, such as pain medications, bone modifying-medications (bisphosphonates or denosumab), anti-emetics or anti-diarrheal medications, transfusions and growth factor support are allowed at the investigator's discretion. Palliative radiotherapy is permitted.

Treatment may be continued after completion of palliative radiotherapy. In this case, sacituzumab govitecan administration should be interrupted one week before the procedure and reinstated no earlier than two weeks after the procedure. In the event that a subject requires surgery, sacituzumab govitecan should be interrupted one week before the procedure if clinically feasible and dosing should be held for 2 weeks after the procedure. Dosing may resume thereafter if the subject is clinically stable. Extensive surgical procedures such as abdominal, cranial surgeries for example, may require suspension of dosing for 4 weeks before dosing may resume to allow for an adequate period for healing.

The study medical monitor must approve continuation of therapy with sacituzumab govitecan prior to resumption of dosing.

Subjects are allowed to receive the COVID-19 vaccine to reduce the risk and complications of COVID-19 infection. Details on the risk assessment and mitigation plan for concurrent administration of the COVID-19 vaccine are provided in [Appendix 2](#).

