10.2.2.2. Reporting Period for Adverse Events

Following initiation of study drug, collect all AEs, regardless of cause or relationship, until 30 days after last administration of study drug and report the AEs on the eCRFs as instructed.

All AEs and clinically significant laboratory abnormalities should be followed until resolution or until the AE is stable, if possible. Gilead may request that certain AEs be followed beyond the protocol-defined follow-up period.

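### The treatment-emergent window closes 30 days after the last dose, but holds can run 35 to 42 days, so a new event that ends treatment can drop out of the tables

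*Protocol*

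**What the plan says.** Four rules run from the last dose:

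- **TEAE definition, protocol.** Section 11.3.3 ends the window "up to the date of last dose of study drug plus 30 days" and applies the same limit to treatment-emergent laboratory abnormalities.
- **TEAE definition, SAP.** Section 6.2 takes events that "begin or worsen on or after the start of study drug through 30 days after the last dose of study drug". It adds worsening to onset but keeps the same end date. It then states: "Only TEAEs will be summarized and will be referred to as AEs hereafter". This covers the tables of AEs leading to permanent discontinuation of study drug.
- **AE collection.** Protocol 10.2.2.2 tells sites to "collect all AEs, regardless of cause or relationship, until 30 days after last administration of study drug".
- **End-of-treatment visit.** Under Protocol 3.4, once treatment has been discontinued, "all subjects must complete an end of treatment (EOT) visit approximately 30 days after the last dose of the study drug".

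Two other rules allow long gaps between doses while the subject remains on treatment:

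- **Table 2 (Protocol 6.3.2.5).** A delay of 2 or 3 weeks for recovery leads to a dose reduction at the first and second occurrence. Discontinuation at the first occurrence applies to "Grade 3 or 4 neutropenia that delays dosing beyond 3 weeks for recovery to" Grade 1 or lower. Similar rows cover other Grade 3 or 4 toxicity.
- **Surgery (Protocol 6.4).** Dosing is interrupted one week beforehand where feasible, and extensive procedures "may require suspension of dosing for 4 weeks before dosing may resume".

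Neither document extends the window to the date treatment is declared ended.

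**The concern.** The window is tied to the last infusion, but the decision to stop can come more than 30 days after it. Between day 31 and that decision the subject is still on study treatment by the protocol's own rules, yet nothing that starts then is treatment-emergent unless a later dose is given. A new complication arising in that interval can be the reason treatment ends and still be missing from the table of AEs leading to discontinuation. Under the SAP the same applies to a separately recorded worsening. Under 11.3.3 it applies to a new laboratory grade increase, for example on the blood test that decides whether dosing can resume.

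Long-term safety is the only objective, and the primary endpoints in Protocol 11.3.1 are the percentages with any AE, any serious AE (SAE) and any laboratory abnormality. The omission can only lower counts.

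**Working it through.** **Inputs**

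- Window: last dose + 30 days (Protocol 11.3.3, SAP 6.2).
- Dosing on Days 1 and 8 of a 21-day cycle (Protocol 6.2).
- Day 8 dose to next Day 1: at least 14 days (Protocol 6.3.2.5).
- An unresolved Day 8 toxicity means the next dose is Day 1 of the following cycle (6.3.2.5), so 21 days after the Day 1 dose.
- Table 2 delay before discontinuation: up to 3 weeks past the scheduled dose.
- Extensive surgery: one week before the procedure, if feasible, and possibly 4 weeks afterwards (6.4). I read the 4 weeks as running from the procedure.

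**Reproducing the plan's own figure.** Next Day 1 is Day 22, and 22 − 8 = 14 days, which matches 6.3.2.5.

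**Days since last dose at the end of a hold** = (days from last dose to next scheduled dose) + 7 × (weeks of delay). For surgery, it is (days from last dose to procedure) + post-procedure hold. Uncovered days = that total minus 30, or 0 if negative.

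| Route | Sum | Day reached | Uncovered days |
|---|---|---|---|
| Last dose Day 8, 2-week delay | 14 + 14 | 28 | 0 |
| Last dose Day 8, 3-week delay | 14 + 21 | 35 | 5 |
| Last dose Day 1, Day 8 omitted, 2-week delay | 21 + 14 | 35 | 5 |
| Last dose Day 1, Day 8 omitted, 3-week delay | 21 + 21 | 42 | 12 |
| Last dose Day 1, 3 weeks counted from the missed Day 8 | 7 + 21 | 28 | 0 |
| Extensive surgery, full week before and 4 weeks after | 7 + 28 | 35 | 5 |
| Extensive surgery, no week before | about 0 + 28 | about 28 | 0 |

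If the next due dose falls inside the pre-surgery week after a Day 8 dose, the surgical hold can reach 14 + 7 + 28 = 49 days.

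**Dependence on a conflict in the protocol.** Section 6.3.2.5 also limits toxicity delays to one week. On that limit the usual totals are 14 + 7 = 21 and 21 + 7 = 28 days, with no gap. The 35- and 42-day toxicity figures therefore rest on Table 2. The surgical figure does not.

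**What falls in the gap.** The Table 2 delay rows describe toxicity present at the scheduled dose, so it has normally begun by day 14 or day 21. That is inside the window, and the event is tabulated even if treatment stops on day 36 or 43. What is lost is a new event (or, under the SAP, a recorded worsening) from day 31 until discontinuation is recorded, in a subject who receives no further dose.

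**Scale per subject.** At the planned maximum of about 200 subjects, each affected subject is 1/200 = 0.5 percentage points in any table row.

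**The case against.** The strongest reply is that this is a corner case in a window on which protocol and SAP agree. Several parts of it stand.

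- **The stopping toxicity is already counted.** A reader might infer that subjects stopped for prolonged toxicity lose the event that stopped them. The documents do not support that: onset fixes the classification, and onset falls before the hold.
- **Not every stop comes late.** Table 2 also stops treatment at a third occurrence, at a Grade 4 infusion reaction and at recurrent Grade 2 or 3 reactions. Protocol 5.3 allows stopping for an AE at any time. A decision at day 36 or later is possible, not general.
- **The surgical hold has no firm 35-day minimum.** The week beforehand depends on feasibility, and the 4 weeks are optional.
- **The any-AE percentage hardly moves.** A subject held for Grade 3 or 4 toxicity already has a TEAE. The exposed results are the discontinuation tables, a first SAE and a new laboratory grade.
- **Collection is wider than 10.2.2.2 suggests.** Table 1 records AEs for the whole study, and 10.2.3 runs AE reporting to the later of 30 days after last dose or start of alternative therapy. SAEs are collected throughout (10.2.2.3), the SAP lists all AEs, and SAP 6.4 summarizes all-cause deaths. It would therefore be too strong to say that non-serious events after day 30 go unrecorded. The sections disagree about whether they are required.
- **Thirty days is pharmacologically long.** With half-lives of 15.3 and 19.7 hours (Protocol 1.3.1.3), 720 hours is about 47 and 37 half-lives. But TEAE status here does not depend on causality, so this does not explain leaving a treatment-ending event out of the discontinuation table.

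Wider collection does not close the gap either, because an event that is recorded but not treatment-emergent still reaches only a listing.

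**Conclusion.** The point holds in a narrow form. The plan's rule can misclassify a new event that ends treatment during a long hold. The uncovered interval is 5 days (last dose Day 8) or 12 days (last dose Day 1, Day 8 omitted) under Table 2, and about 5 days for a full extensive-surgery hold. It affects only subjects who never resume.

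The conclusion assumes that Table 2's delays apply despite the one-week limit, that the delay after an omitted Day 8 is counted from the next Day 1, and, for surgery, that the full hold is used.

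A reader might multiply the gap by an assumed monthly AE rate and quote a percentage of subjects affected. The documents give neither an AE rate for subjects off drug nor the frequency of these routes, so no such figure can be supported. The effect on overall percentages is unknown and probably small. The direction is known: the omission can only lower counts.

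The end-of-treatment visit has a related but lesser problem. It is due about day 30 and is to follow discontinuation, so it cannot be on time when the decision comes at day 36 or 43. The visit's timing is approximate, with no stated tolerance.

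**What to change.** 1. **Protocol 11.3.3 (AE and laboratory definitions) and SAP 6.2.** End the window at the later of last dose + 30 days and the date permanent discontinuation is recorded. At minimum, count any AE recorded as leading to discontinuation of study drug as treatment-emergent. Keep the last dose + 30 days count as a sensitivity table.
2. **Protocol 10.2.2.2.** Require AE collection to at least the same date, and reconcile it with Table 1 and 10.2.3. Do not cut collection at the start of new anti-cancer therapy, because 10.2.2.3 and 10.2.3 run reporting to or beyond that point.
3. **Protocol 3.4 and Table 1.** Place the end-of-treatment visit about 30 days after the last dose or at the decision to discontinue, whichever is later.
4. **Protocol 6.3.2.5.** The one-week delay limit and the 2- to 3-week delays in Table 2 contradict each other. The sponsor must reconcile them; this review takes no position on which should apply.

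The cost is wording in two documents and one extra table. Slightly more AEs may be counted, and the window will differ in length between subjects, which the report should state. No dosing rule changes under items 1 to 3.
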